8.4 Precautions and Warnings, Prohibited Medications/Treatments and Restrictions

8.4.1 Precautions and Warnings

- The device must not be used if the expiry date has lapsed, if the packaging or contents are damaged, or if the gel in the syringe appears inhomogenous and/or cloudy
- The device should not be injected into blood vessels, bones, tendons, ligaments, nerves, muscles or naevi
- Immediately stop the injection if a subject exhibits any signs or symptoms associated with injection into a blood vessel, such as changes in vision, signs of a stroke (including sudden difficulty speaking, numbness or weakness in their face, arms or legs, difficulty walking, face drooping, severe headache, dizziness, or confusion), white appearance (or blanching) of the skin, or unusual pain during or shortly after the procedure
- In case of a vascular event, emergency treatment must be sought, and high dose hyaluronidase (Alam et al., 2008), vigorous massage and heat (gauze with hot water) should be applied. In addition, topical 2% nitroglycerin paste may encourage vasodilatation (Belazay et al., 2015)
- The device should never be placed in contact with quaternary ammonium compounds (such as benzalkonium chloride solutions) or with medical-surgical instruments that have been in contact with these substances

Upon completion of device administration

- After injection the investigator may apply a light massage for uniform distribution of the filler
- Application of ice packs for 5-10 min. post injection is optional and may reduce redness
 and swelling; this have to be recorded in the clinical investigation eCRF(s) along with any
 other concomitant medication/treatment
- The subject should be requested to stay in the office for a period of at least 30 minutes after the injection to assess pain following injection and to detect possible blanching caused by arterial occlusions

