9.2.2 Exclusion Criteria

Subjects who meet **ANY** of the following criteria are **NOT** eligible for a repeat-treatment:

- CPH-301-201200F
- Occurrence of an SAE or adverse event of special interest (AESI; i.e., changes in vision [loss
 of vision, blurriness, double vision, pain in or around the eye, blindness, blind spots,
 problems moving the eyes, change in peripheral vision], skin changing color around the
 eyelids or around the site of injection) during or after the initial injection and/or touch-up
 injection
- 2. Subjects who experienced visual changes or other serious medical conditions during or after the initial/touch-up injection
- 3. Subjects who have one of the following assessments during the visual examinations:
 - Snellen acuity test worse than 20/40 (with corrective eyewear, if applicable)
 - abnormal confrontational visual field test
 - abnormal ocular motility test
- 4. Subjects who became pregnant since start of the study or are planning to become pregnant during the clinical investigation
- 5. Known human immune deficiency virus-positive individuals
- 6. Presence of infectious, inflammatory or proliferative cancerous or pre-cancerous lesions in the area to be treated
- 7. Development of recurrent herpes simplex in the treatment area since study start
- 8. Development of any autoimmune or connective tissue disease since start of participation in the study, or current treatment with immunomodulating therapy
- 9. Development of uncontrolled (or instable) diabetes mellitus or any other systemic disease since study start
- 10. Development of a bleeding disorder since study start or use of anticoagulant, antiplatelet or thrombolytic medication from ten days pre- to three days post injection
- 11. Planned dental/oral surgery or modification (bridge-work, implants) within 2 weeks prior to injection and to a minimum of four weeks post injection
- 12. Any medical condition prohibiting the inclusion for repeat treatment according to the judgement of the treating investigator

9.3

Subject Withdrawal and Discontinuation

Each subject has the right to withdraw his/her consent to participate in the clinical investigation at any time and without giving reasons.

Subjects may be discontinued for the following reasons:

- Lost to Follow-Up
- Consent withdrawal (the treating investigator must try to find out and document the reasons for withdrawal of consent)

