Treatment: Initial, touch-up with the assigned device following randomization scheme will be applied according to this CIP. The repeat-treatment will be performed with Princess[®] FILLER Lidocaine on both NLFs.

- Adverse events: Occurrence of adverse events will be collected at each visit after the initial treatment at Baseline (Visit 2), from Visit 2 to Visit 9a, 9b or 9c included (for more information, see Section 12).
- Urine pregnancy test: Required in women of childbearing potential only, including those who are postmenopausal for less than twelve months. An urine pregnancy test (dip stick) will be performed at Screening (Visit 1), prior to initial treatment (Day 0/Visit 2), prior to touch-up treatment (Week 2/Visit 3a) and prior to repeat-treatment (Week 36/Visit 6, Week 48/Visit 7 or Visit 7c).
- Weight measurement: at Baseline (Day 0/Visit 2), at Visit 3a, 3b, 3c, 4 and 5, as well as at Visit 6, Visit 7 or Visit 7c upon evaluation for repeat-treatment; as well as Visit 8a/8b/8c or Visit 9a/9b/9c; weight measurement should be done to the nearest 0.1 kg and with the subjects standing barefoot and wearing light indoor clothing.
- Subjects' daily safety diary: to be dispensed to each subject at the end of each treatment session (and additionally at Week 4/Visit 3b for subjects having received touch-up treatment at Week 2/Visit 3a) in order to record injection site reactions, as well as the incidence of adverse events and AEs associated with the unintended intravascular injection; to be collected and reviewed two and four weeks after initial-/touch-up treatment (and additionally at Week 6/Visit 3c), and four weeks after repeat-treatment.

The diary will include the following adverse events:

- Changes in vision (i.e. loss of vision, blurriness, double vision, pain in or around your eye, blindness, blind spots, problems moving the eyes)
- Skin changing color around the eyelids
- o Crusty or scabby skin around the eyelids
- Headache
- o Fever
- Dizziness
- Confusion
- Weakness or numbness in the arms or legs
- o Changes to consciousness or alertness
- O Difficulty speaking/speech impairment

- Face droop
- Changes to chewing and drinking
- o Discomfort and discomfort with palpation
- Sensitivity to hot/cold liquids and foods

Furthermore, the subject diary will include specific instructions to seek immediate medical attention if any of the above symptoms or signs is observed.

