12.1 Definitions of Adverse Events and Adverse Device Effects

Adverse Event (AE)

An AE is defined as any untoward medical occurrence, unintended disease or injury or any untoward clinical signs in subjects, users or other persons. This definition includes events whether or not related to the IMDs and those events related to the procedures involved.

Adverse Device Effect (ADE)

An ADE is defined as an AE that is related to the use of the IMDs. This includes any AE resulting from insufficiencies or inadequacies in the IFU, the deployment, the implantation, the installation, the operation, or any malfunction of the IMDs. In addition, this includes any event that is a result of a use error or intentional misuse of the IMDs.

Those AEs occurring after provision of informed consent and prior to application of the IMDs will be recorded as part of the medical/aesthetic procedures history. Any medical condition that is present at the time that the subject is screened should be also considered as medical/aesthetic procedures history and not recorded as an AE (see Section 10.9). However, if the condition deteriorates at any time from date of administration of the IMDs during the clinical investigation, it should be recorded and reported as an AE.

For a list of anticipated AEs and anticipated ADEs please refer to Section 6.1. In addition, the following events could specify as Adverse Events of Special Interest (AESI);

- Changes in vision (i.e. loss of vision, blurriness, double vision, pain in or around your eye, blindness, blind spots, problems moving the eyes, change in peripheral vision)
- Skin changing color around the eyelids or around the site of injection

Serious Adverse Event (SAE)

An SAE is defined as an AE meeting one or more of the following conditions:

- led to death
- led to serious deterioration in health of the subject that either resulted in:
 - o a life-threatening illness or injury, or

- o a permanent impairment of a body structure or a body function, or
- o in subject hospitalization or prolonged hospitalization, or
- o medical or surgical intervention to prevent life-threatening illness or injury or permanent impairment to a body structure or a body function
- led to fetal distress, fetal death, or a congenital abnormality or birth defect
- is an important medical event

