12.4 Adverse Event Monitoring and Assessment

Subjects will be monitored for AEs throughout the clinical investigation from signing the ICF until the final visit. Should an SAE occur after the final visit, which is considered at least possibly related to the IMD or procedure, such events should always be reported to Croma-

Pharma GmbH or its representative, even after the end of the clinical investigation.

Subjects will be questioned concerning their well-being at all visits from screening through to

the final visit. Furthermore, subject diaries will be provided to the subjects, and they will be

instructed to note Injection site reactions, AEs and AESI. In addition, subjects will be

encouraged to spontaneously report any AEs, ADEs or SAEs. Any subject with an AE, SAE or

clinically significant abnormal test result will be evaluated by the treating investigator and will

be treated and/or followed up as per local clinical practice. A physician, either at the

investigative site or at a nearby hospital emergency room, will administer treatment for any

SAEs. Where appropriate, medical tests and examinations may be performed to ensure that an

AE has fully resolved.

If an Injection site reaction is not resolved at the time the by the time the diary is returned after

4 weeks (after treatment, touch-up treatment, retreatment), the injection site reaction might be

classified as an AE s per investigator discretion.

By default, AEs ongoing at the termination visit will not be followed-up. However, SAEs which

are ongoing at the End of Clinical investigation visit will be followed-up until recovery or

normalization of changed laboratory parameters, or until the treating investigator determines

that the subject's condition is stable or a plausible explanation has been provided, whichever

occurs first.

All subjects excluded from repeat-treatment should continue to be followed until the resolution

of all ongoing AEs, regardless of device relatedness.

Adverse events will be coded using the current version of the Medical Dictionary for Regulatory

Activities (MedDRA). Whenever possible, a specific disease or syndrome, rather than

STRICTLY CONFIDENTIAL

CPH-301-201200F

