12.4.1 Unanticipated Adverse Device Effects Reporting

A UADE is "any serious adverse effect on health or safety or any life-threatening problem or death caused by, or associated with, a device, if that effect, problem, or death was not previously identified in nature, severity, or degree of incidence in the investigational plan or application (including a supplementary plan or application), or any other unanticipated serious problem associated with a device that relates to the rights, safety, or welfare of subjects" (21 CFR 812.3[s]).

Investigators should report UADEs to the sponsor and to the IRB as follows: Investigators are required to submit a report of a UADE to the sponsor and the reviewing IRB as soon as possible, but in no event later than 10 working days after the investigator first learns of the event (21 CFR812.150[a][1]).

Sponsors must immediately conduct an evaluation of a UADE and must report the results of the evaluation to FDA, all reviewing IRBs, and participating investigators within 10 working days after the sponsor first receives notice of the effect (21 CFR 812.46[b], 21 CFR 812.150[b][1]).

Clinical investigation stopping rules in case of vascular occlusion:

Special care will be taken in case of vascular occlusion which is a rare, but serious, adverse event; this encompasses vascular embolic events which may lead to skin necrosis, vision loss or stroke.

In the event that such a complication occurs, the enrollment and treatment at the investigational site will be suspended and a root cause investigation has to be conducted to determine the cause of the event. If the investigator didn't properly follow the treatment procedure, he/she will be re-trained before being allowed to recruit further subjects.

In case this event was unanticipated and the investigator did follow the treatment procedure correctly, the entire clinical investigation has to be immediately suspended and no subjects

15 Mar 2021

should be enrolled until the event can be properly characterized and an appropriate treatment strategy to avoid this unanticipated event can be devised.

For received reports containing any event relating to incidences of visual distributions, in the form of a site query ('Device Safety Query for Additional Information' form, see SMP 9.5.4), the following information must be urgently requested:

- Depth of injection (i.e. subcutaneous or supraperiosteal)
- The injection volume
- The symptoms that were observed

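### The diary's urgent-care list names skin colour change only around the eyelids, although the protocol's AESI definition also names the injection site; a minor patient-safety alignment

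*Protocol*

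**What the plan says.** Protocol Section 10.9 specifies the daily safety diary. It lists 14 events, and the closing sentence ties one urgent instruction to the whole list: "the subject diary will include specific instructions to seek immediate medical attention if any of the above symptoms or signs is observed". Two of the 14 items concern skin. One is "Skin changing color around the eyelids"; the other is crusting or scabbing, also at the eyelids.

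Section 12.1 defines the skin AESI more widely: "Skin changing color around the eyelids or around the site of injection". SAP Section 9.3 uses the same two locations. Repeat-treatment exclusion 1 in Section 9.2.2 ("Occurrence of an SAE or adverse event of special interest") also spells out both. Section 12.4 says that subjects given the diary are "instructed to note Injection site reactions, AEs and AESI".

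Two other places bear on why the injection site matters. Section 8.4.1 tells the injector to stop on signs of injection into a vessel, including "white appearance (or blanching) of the skin, or unusual pain during or shortly after the procedure". The stopping rule in Section 12.4.1 says of vascular occlusion that "this encompasses vascular embolic events which may lead to skin necrosis, vision loss or stroke".

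**The concern.** The stopping rule names three outcomes of occlusion. The diary's urgent list has signs for vision loss and for stroke. For skin it has signs only at the eyelids, while the filler goes into the nasolabial fold. The protocol thus recognises colour change at the injected site as an AESI and blanching as a vascular sign, but does not put either on the list that tells a subject at home to get help quickly.

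Timing is what could make this matter. The observation period in Section 8.4.1 (at least 30 minutes) can catch only early blanching. The comparator label (Protocol Appendix 3, Postmarket Surveillance) gives onset of vascular occlusion from immediate to within a week. For a sign that appears at home, a named trigger helps the subject recognise it.

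**Working it through.** The protocol gives no figure to reproduce. The check is a comparison of texts, followed by the contact schedule.

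**Skin signs, place by place**

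| Place | Eyelids | Injection site |
|---|---|---|
| Protocol 10.9, diary list with urgent instruction | yes | no |
| Protocol 12.1, AESI definition | yes | yes |
| Protocol 9.2.2, repeat-treatment exclusion 1 | yes | yes |
| SAP 9.3, AESI list | yes | yes |
| Protocol 8.4.1, signs of vessel injection (for the injector) | not stated | blanching of the skin, no location given |

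One element of the AESI definition, colour change at the injection site, is missing from the diary list. No other sentence in the protocol or SAP attaches the diary's urgent instruction to it. Section 12.4 has AESIs noted in the diary, but attaches no instruction about urgency.

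**Contact schedule** (Sections 10.11.3, 10.11.11, 10.11.12 and 10.13; treatment day = Day 0)

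- Day 3 call, ±24 hours: Day 2 to 4.
- Week 2 visit, ±3 days: Day 11 to 17.
- First visit after repeat-treatment, 4 weeks ±5 days: Day 23 to 33.

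Gap = day of next scheduled contact − day of call.

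- Initial treatment: shortest 11 − 4 = 7 days, longest 17 − 2 = 15 days, nominal 14 − 3 = 11 days.
- Repeat-treatment: shortest 23 − 4 = 19 days, longest 33 − 2 = 31 days, nominal 28 − 3 = 25 days.
- Touch-up (given on Day 11 to 17 after initial treatment, next visit at Week 4, Day 23 to 33): shortest 23 − (17 + 4) = 2 days, longest 33 − (11 + 2) = 20 days, nominal 28 − 17 = 11 days.

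For an onset on Day 7, the end of the label's range, the shortest wait for the next scheduled contact is 11 − 7 = 4 days after initial treatment and 23 − 7 = 16 days after repeat-treatment, unless the subject acts sooner. These numbers describe scheduling. They do not measure risk.

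**The case against.** The strongest answer is that an urgent route already exists. Section 6.1 says subjects are told to contact the treating investigator immediately about any health concern between visits. That leads to a site which, under Sections 6.1 and 8.4.1, must hold a treatment protocol for unintended vascular injection. This stands, and it reduces the point to one unnamed example in one list.

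Other controls also stand. The Day 3 call asks about adverse events in general; vision and stroke are its added probe, not its limit. Pain scoring keeps contact to 60 minutes after initial and repeat-treatment (Section 10.4). The diary also records injection site reactions, so colour change at the fold can be captured there. The diary page is not in the documents and may already carry the item. Many of the label's occlusion cases followed injection into the glabella, nose and periorbital area, outside the labelled indications, so its one-week range may not describe nasolabial folds.

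There is also a possible reason for a narrow list. In the label's 36 folds treated with the comparator, bruising was reported in 27 (75%) and discoloration in 22 (61%). An urgent item worded simply as colour change at the injection site could bring in many subjects with ordinary bruising. That is an argument about wording; it does not justify leaving the sign out.

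A reader might also infer that the list has its priorities reversed, because it includes "Discomfort and discomfort with palpation" without a severity qualifier. The documents do not support that. The item stands between chewing and drinking and sensitivity to hot or cold foods, so it may mean oral discomfort. If it does cover the fold, it is a broad safety net, and narrowing it would have a safety cost of its own.

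**Conclusion.** The mismatch is real and is visible in the current text: the list carrying the diary's urgent instruction omits the injection-site part of the skin AESI. Its size is one missing sign, in a list backed by a general instruction to call at once and by adverse event questioning on Day 3. It is a minor patient-safety alignment.

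A reader might infer that a subject with a blanched fold has no urgent route, or that such events would go unrecorded and the subject could pass to repeat-treatment. The documents do not support either reading. Section 6.1 supplies the route; Section 12.4 and the injection-site-reaction part of the diary supply the recording; and the Section 9.2.2 exclusion turns on whether the event occurred, not on whether the diary listed it.

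The conclusion assumes that the diary page follows Section 10.9 as written and that subjects are guided more by a named sign than by a general instruction. Neither can be checked from the documents. The frequency of late occlusion in nasolabial folds is not given, so no number of affected subjects can be stated. No effectiveness analysis is touched.

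**What to change.** Extend the skin item in Section 10.9 to the Section 12.1 wording, "Skin changing color around the eyelids or around the site of injection". On the subject's page, express the injection-site part in lay terms: white or blanched skin, or an unusual skin colour other than ordinary bruising or redness. Add the same item to the Day 3 call after initial, touch-up and repeat-treatment, beside vision and stroke. The sponsor's medical team should set the final wording. If the diary page in use already names the sign, only the protocol text needs to follow it.

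The cost is a revised diary page and call script, a change to one protocol item, and IRB handling. No visit or procedure is added. Some extra contacts for bruising should be expected; the qualifier is there to limit them, though subjects will not always make the distinction correctly.

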10.10 Factors that may Compromise the Outcome

There are no anticipated factors that may compromise the outcome. Substantial body weight changes (more than 10% change from Baseline), UV and sunlight exposure, as well as acne may affect the results. Subjects with unhealthy skin will not be included (see Section 9.1). Subjects will be advised to abstain from prolonged UV exposure for one week after the treatment (see Section 8.4.3) or from excess body weight gain or loss.

10.11 Schedule of the Clinical Investigation

An overview of the schedule of the investigation is provided in Section 2.1. Subjects who have signed the ICF will be considered enrolled.

10.11.1 Screening (Visit 1)

After written informed consent is obtained, the following procedures and/or assessments will be performed at Screening (Visit 1), Day -14 to -3:

- Evaluation of inclusion and exclusion criteria (eligibility assessment)
- Urine pregnancy test in women of childbearing potential only, including those who are postmenopausal for less than twelve months
- Demography (date of birth, sex, race and ethnicity)
- Fitzpatrick skin type
- Medical history (including information on prior facial aesthetic or surgical procedures)
- Live evaluation of nasolabial fold severity by treating investigator in conjunction with the independent blinded evaluating investigator using the 5-point NLF-SRS
- Photography

10.11.2 Baseline (Visit 2)

The following procedures and/or assessments will be performed at Baseline (Visit 2), Day 0:

- Body weight measurement
- Visual examinations (including Snellen visual acuity, confrontational visual fields and ocular motility) prior to- and 30 min after the treatment (see Section 10.8)
- Evaluation of eligibility criterion based on visual examinations
- Urine pregnancy test in women of childbearing potential only, including those who are postmenopausal for less than twelve months (prior to treatment)
- Randomization (prior to treatment)
- Treatment (initial treatment)
- Live assessment of nasolabial fold severity by treating investigator using NLF-SRS (prior to treatment)
- Live assessment of nasolabial fold severity by the independent blinded evaluating investigator using NLF-SRS (prior to treatment)
- Photography (prior to treatment)
- Evaluation of pain assessment by the subject using the adapted NPRS
- FACE-Q subject appearance appraisal questionnaire ("appraisal of nasolabial folds") (prior to treatment)
- Dispense of subject diary
- Assessment of injection volume
- AEs (prior to treatment)
- Concomitant medications/procedures (prior to treatment)

10.11.3 Phone Contact after Visit 2

The following assessments will be performed at Day 3 (± 24 hours) after Visit 2:

- AEs including if subjects are experiencing or have experienced any signs/symptoms of vision changes or stroke since the injection
- Concomitant medications/procedures

